### **Innovation**

The available data on GLN outlined above supports the need for a rigorous, double-blind clinical study to obtain critically needed pilot data on the efficacy of enteral GLN supplementation in pediatric SBS. This proposed study represents collaborative, multidisciplinary, multisite, comparative effectiveness clinical research. The rigorous nature of this trial of GLN supplementation in SBS infants is innovative compared to previous studies; our subject group is also more homogeneous, as we limit enrollment to children with NEC, omphalocele, gastroschisis and those with atresia as the primary cause of SBS. Our proposed design incorporates important clinical outcome measures (incidence of BSI and somatic growth parameters) to provide needed information on GLN efficacy in pediatric SBS. The data, in turn, will inform the design of subsequent definitive multicenter Phase III studies. In addition, to follow-up on our studies of GLN-induced upregulation of stool and mucosal sIgA in rat models of SBS, we have measured stool sIgA in SBS children in a previous prospective trial and propose here to evaluate the impact of GLN on stool sIgA as a secondary index of enteral GLN efficacy.

**The study of the gut microbiome in pediatric SBS and the response to GLN on these microbial populations is innovative.** Commensal microbes may have a role in the immune conditioning of the gut, and may influence subsequent immune responses in neonates. The intestinal microbiome may also be important for physiologic gut absorptive and barrier functions; small bowel bacterial overgrowth and/or altered luminal microbiota (e.g. due to anatomic disruptions after intestinal resection, dysmotility, stasis, etc.) may represent a potentially crucial, but as yet uncharacterized pathophysiologic factor in SBS. The underlying disease (NEC), malnutrition, and illness-associated immunodeficiency have been hypothesized to promote the proliferation of luminal bacteria. Further, effects of altered nutrient intake in SBS on the microbiome are unknown. **Therefore, in specific aim #3, we will comprehensively assess the gut luminal microbiome in pediatric SBS patients versus controls to: 1) correlate alterations in luminal bacteria populations with BSI risk; and 2) determine whether GLN supplementation influences the gut microbiome and concomitant microbial pathogenesis of BSI.**

Collaborators, Drs. [name] and [name] have developed molecular tools with which to study naturally occurring microbial communities without the requirement for preliminary culture. **A number of these methods are centered on analysis of bacterial 16S ribosomal RNA gene (rDNA) sequences (see Figure 1, below)** which vary from species to species and thus can be used as molecular ‘bar-codes’ for species identification. rDNA can be PCR amplified with pan-bacterial primers from genomic DNA isolated directly from specimens, without need for prior culture of resident microorganisms (Figure 1, step A). Advances in sequencing technology, such as the massively parallel GS-FLX pyrosequencing platform of Roche 454 Life Sciences, Inc. dramatically increased throughput compared to the previous generation of sequencers (Figure 1, step B). This platform was successfully deployed in a pilot study of the pediatric SBS microbiota.

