**Data collection:** During CNC/clinic visits (baseline, days 30, 60, 90, 120, 150 and 180) as described above, each child will have weight, length mid arm circumference and head circumference measured in duplicate. These measurements will be done by a trained member of the study staff at each center. The individual at each site will be trained to perform these

measurements according to standard methods previously described. Institutional scales, length boards and measuring tapes will be used at each center.

**Expected results:** We expect that SBS children on enteral GLN supplementation will have more rapid growth as measured by the parameters above. The group with no BSI or decreased BSI (2 episodes) during the study period is expected to have a greater increase in growth parameters compared to the group with > 2 BSI.

**Hypothesis 3:** The gut luminal microbiome is altered in pediatric SBS versus non-SBS controls, correlates with BSI and is altered by enteral GLN supplementation.

**Specific Aim 3:** To comprehensively assess the gut luminal microbiome (using state-of-the art molecular methods) in Aim 1 SBS patients versus non-SBS, age-matched control subjects (primary endpoint), to correlate major bacterial dynamics present in the lumen with BSI due to specific microbes and to explore whether the gut luminal microbiome is altered by enteral GLN treatment.

**Primary outcome:** Increased *K. pneumonia* and *E. faecalis* in the gut microbiome of SBS infants with BSI.

**Secondary outcome:** Alteration in other commensals in the gut luminal microbiome of SBS infants.

**Subjects:** Infants recruited in specific aim 1 (n=48 – subjects- 36; controls- 12) Healthy age matched infants (n=12) will be recruited from the Gastroenterology and surgery clinics.

**Sample Procurement:** Stool samples (~500 mcg), will be obtained from infants' diapers or ostomy bags. Stool specimens will be collected prospectively during visits at baseline, days 30, 60, 90, 120, 150 and 180. **Stool will also be collected whenever the patient has a BSI.**

The controls (12 healthy infants) will have serial stools collected on 4 occasions, each separated by 60 days (baseline, days 60, 120 and 180).

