- 8) Intestinal microbial groups (e.g., species, genera) will be correlated with the treatment or control arms of the GLN supplementation trial and with bacteria identified during any diagnosed BSI. The frequency of rRNA sequences will be interpreted as the relative abundances of organisms in samples of stool and standardized by gram of stool weight. Bacteria present in specimens will be preliminarily identified by use of the Naïve Bayesian Classifier Tool of the Ribosomal Database Project. The strength of association of individual microbial groups with treatment arms and/or main outcome measures will be measured by comparing the abundances of these groups using the non-parametric Kruskal-Wallis test. Experimental reproducibility and inter- and intra-individual similarities in microbial populations will be assessed by calculating and comparing the sequence-abundance-based Morisita-Horn index. In all statistical analyses 2-sided *p*-values less than 0.05 will be considered statistically significant. Results will be corroborated through the phylogeny-based UniFrac metric, which assesses population-wide differences in microbial lineages between different groups of subjects (SBS vs. control). Stool-associated bacteria collected at BSI incidence will be compared to the species identified on blood culture to determine whether intestinal bacteria are potential sources for BSI. Alternatively, absence of particular species from the stool at the time of BSI diagnosis will indicate that lack of specific bacterial species from the stool predisposes to BSI. Tissue samples collected during endoscopy or surgery and intestinal fluid aspirated during endoscopy will be analyzed in parallel with stool samples in order to assess the use of stool samples as proxies for intestinal samples. Patterns will also be reviewed to assess for relationships to enteral feeding rate.

These methods have been used and demonstrated in 2 published studies by one of the collaborators/co-investigators.

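### Aim 3 asks about BSI risk, but its BSI comparison does not separate stools taken before the infection from those taken at or after it

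*Combined protocol and SAP*

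**What the plan says.** - **Purpose.** Background, Innovation: one of two stated purposes of Aim 3 is to "correlate alterations in luminal bacteria populations with BSI risk".
- **Primary outcome.** Section X, Specific Aim 3: increased *K. pneumonia* and *E. faecalis* "in the gut microbiome of SBS infants with BSI". No sampling time relative to the BSI is given.
- **Stools available.** Section X: "Stool specimens will be collected prospectively during visits at baseline, days 30, 60, 90, 120, 150 and 180". In addition, "Stool will also be collected whenever the patient has a BSI".
- **Test.** Section XIII, Aim 3: the link between microbial groups and treatment arms and/or main outcome measures "will be measured by comparing the abundances of these groups using the non-parametric Kruskal-Wallis test", at a two-sided 0.05 threshold. The text does not say which stools enter or how repeated stools from one infant are combined.
- **BSI-time stool.** Section XIII gives it one explicit use: "Stool-associated bacteria collected at BSI incidence will be compared to the species identified on blood culture". It then adds that absence of a species at diagnosis "will indicate that lack of specific bacterial species from the stool predisposes to BSI".

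**The concern.** A risk association requires the exposure to be measured before the event. A BSI can itself change the stool, through the illness, interrupted feeding, a hospital stay and treatment. For an infant first infected on day 40, the stools from days 60 to 180 could all carry such changes, and nothing in the plan keeps them out of the comparison with uninfected infants. The sentence on predisposition goes further, because it reads a cause from a sample taken when the outcome has already occurred.

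Two things are at stake. A taxon with no bearing on later infection could be reported as a risk factor, and a real signal before infection could be diluted by later stools. The protocol says that these data will inform later Phase III trials, so a mislabelled taxon could carry forward.

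**Working it through.** **Inputs from the documents.** BSI rates of 75% and 30% over 6 months, 18 enrolled and 16 completing per arm, one-sided 10% Fisher's exact test, at least 85% power (Section XIII, Sample size). Seven scheduled stools on days 0, 30, ..., 180 (Section X).

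**Assumptions not in the documents.** Constant BSI hazard in each arm, complete stool collection, and a baseline stool that precedes the first on-study BSI.

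**1. The plan's own figure.** Power is the sum of Bin(x; 16, 0.75) × Bin(y; 16, 0.30) over all pairs (x, y) with one-sided Fisher p ≤ 0.10. This gives 85.7%, so the stated figure of at least 85% is reproduced. The plan gives no figure for stools before or after a BSI.

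**2. Scheduled stools after the first BSI, per infant with a BSI.** With 180-day risk p, the chance of a first BSI before day 30k is 1 − (1 − p)^(k/6). Given a BSI within 180 days, the expected number of later scheduled stools is

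E = [6 − Σ(1 − p)^(k/6)] / p, for k = 1 to 6.

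- p = 0.75: Σ = 0.794 + 0.630 + 0.500 + 0.397 + 0.315 + 0.250 = 2.886. E = 3.114 / 0.75 = 4.15 of 7 (59%).
- p = 0.30: Σ = 0.942 + 0.888 + 0.837 + 0.788 + 0.743 + 0.700 = 4.898. E = 1.102 / 0.30 = 3.67 of 7 (52%).

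**3. Pooled, 18 per arm.** Cases: 18 × 0.75 + 18 × 0.30 = 13.5 + 5.4 = 18.9, leaving about 17 non-cases. Scheduled case stools: 18.9 × 7 = 132.3. After the first BSI: 13.5 × 4.15 + 5.4 × 3.67 = 75.9, or 57%.

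**4. Sensitivity to timing and counting.**

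| Setting | Share of case stools |
|---|---|
| Constant hazard, scheduled stools only | 57% after |
| Uniform timing, scheduled stools only | 3.5 / 7 = 50% after |
| First BSIs near day 135, scheduled stools only | 2 / 7 = 29% after |
| Constant hazard, one BSI-time stool added and counted as at or after | (75.9 + 18.9) / 151.2 = 63% |
| Constant hazard, BSI-time stool in the denominator only | 75.9 / 151.2 = 50% after |

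**5. Effect on false positives (simulation).** 16 per arm, exponential time to first BSI, intra-infant correlation 0.5, no difference before BSI. Kruskal-Wallis on each infant's mean of scheduled stools, cases against non-cases, at 0.05. The size and duration of the shift, and the use of infant means, are assumptions.

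| Shift in log abundance after BSI | 30 days | 60 days | Rest of follow-up |
|---|---|---|---|
| 1 SD | about 6% | about 14% | about 47% |
| 0.5 SD | about 5% | about 8% | about 17% |

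Repeat runs of the 1 SD row ranged over 6–8%, 14–16% and 47–50%. If the BSI-time stool is added to each case's mean and is already shifted by 1 SD, the rates rise to about 14%, 24% and 57%.

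**6. What a restriction would leave.** 132.3 − 75.9 = 56.4 scheduled case stools precede the first BSI, about 3.0 per case. Under the assumptions above, every case keeps at least its baseline stool, so one stool per case before BSI is feasible.

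**The case against.** The strongest reply is that Section XIII is silent on the stool window, and silence is not a choice. A reader might infer that the plan prescribes averaging all of an infant's stools, or that it deliberately uses later stools as evidence of what came before. The documents say neither. That part of the objection stands, and the infant-mean simulation is an illustration of one permitted analysis. What takes the point beyond missing detail is the predisposition sentence, which does state an inference from a stool taken at the outcome.

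Other points on that side:

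- **The aim is worded as correlation, and this is a pilot.** True of most passages. But Innovation says risk, Section X makes the infants-with-BSI comparison a primary outcome, and Section XIII applies a 0.05 threshold.
- **The blood-culture comparison is already tied to the event.** It is, but it traces the source of an infection. It has no uninfected comparator and does not address risk.
- **Short shifts matter little.** This stands: at 0.5 SD for 30 days the error rate stays near 5%.
- **BSI recurs.** A stool after the first BSI may precede a second, and infants with a BSI before enrolment are not excluded, so a baseline stool may itself follow an infection. Both points stand and limit how clean any restriction can be.

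**Conclusion.** The concern holds as a defect of time order in one analysis. The plan asks about risk, does not separate stools before the BSI from those at or after it, and draws a predisposition inference from BSI-time stools. It should be corrected before analysis.

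The size is conditional. The 57% share is an expectation from the plan's own rates and schedule under a constant hazard. A reader might take it as a fixed property of the trial that most case stools follow the infection, but it is 50% under uniform timing and 29% if first BSIs come late. The false-positive rates of about 6%, 14% and 47% depend on a 1 SD shift and an infant-mean analysis that the documents do not specify.

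A reader might also conclude that the trial cannot answer its question about BSI risk. That does not follow: serial stools and BSI dates are collected, so a time-ordered analysis is possible. The comparison of SBS infants with controls and the question of a GLN effect on the microbiome do not depend on this point.

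**What to change.** In Section XIII, Aim 3:

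- State that the BSI-risk association compares each case's last scheduled stool before the first on-study BSI with stools taken at the same visit from infants still BSI-free, accounting for treatment arm. Same-visit comparators matter because the microbiome may change with age: with randomly chosen comparator stools, an assumed age trend of 1 to 2 SD over 180 days alone raised the error rate to about 10–20%. The same-visit version was not simulated here.
- A Cox model for time to first BSI with the latest stool as a time-updated covariate is an optional alternative. With about 17 to 19 events it can carry little else.
- Report stools taken at or after a BSI separately, as descriptive or source-tracing data.
- Delete the inference that absence of a species at BSI diagnosis predisposes to BSI.
- Note any BSI before enrolment when interpreting baseline stools.

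In Section X, reword the Aim 3 primary outcome as abundance before BSI.

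**Cost.** No new samples, visits or change to randomisation, since BSI dates and visit-dated stools are already collected. Fewer stools enter this one analysis: one per case, from about 56 of 132 scheduled case stools that precede the first BSI at 18 per arm. The wording of a primary outcome changes, so the amendment should precede any look at the microbiome data by BSI status.

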**Figure 1: Analysis of human microbiome through culture-independent rRNA sequence analysis**

Quantitative analysis of the human microbiome data will be done as

follows: DNA sequences will be phylogenetically compared to rDNA sequence databases (e.g. GenBank which stores >2,000,000 16S entries) to relate newly generated rDNA sequences to those of known organisms and thereby identify the source organisms (Figure 1, steps C and D). The results are a snapshot census of the microbial community within a specimen (Figure 1, step E) which provides a reference point from which physiology and lifestyle can be inferred. Many rRNA-based methods demonstrated the merits of monitoring intestinal microbes to gain insights into how commensals contribute to gastrointestinal pathology, including antibiotic

associated diarrhea and inflammatory bowel disease. **Analogous to IBD, large-scale changes in the enteric microbiota of SBS patients may exacerbate the breakdown of gut mucosal immune homeostasis and barrier function, and thus contribute to BSI.**

#### **Updated data on glutamine use and new procedures not in original grant**

Following the submission and approval of this application, more data regarding the potential benefit of enteral GLN in promoting growth and stimulating immune response against infections has not been published. There were no new relevant trials in humans using enteral GLN in infants. There is follow up data on infants enrolled in earlier trials showing that those who received enteral GLN had decreased for developing gastrointestinal infections and dermatitis likely due to the impact of GLN on the immune system^83. However, new animal models suggest GLN supplementation may be useful in reducing the severity of weaning-related gastrointestinal infections, by reducing the mucosal cytokine response and altering intestinal barrier function. As a result of this we are proposing to evaluate as part of specific aim 1 the serum levels of anti-flagellin and anti-liposaccharide(LPS) immunoglobulin (Ig) G levels in the infants with SBS. These antibodies are markers of response to bacterial antigen and improve with advancing enteral nutrition. This proposal seeks to evaluate the impact of enteral L-GLN on the mucosa's immune response by measuring fecal IgA.

#### **IV. Duration of Study**

This anticipated duration to complete the study is 3 years (enrollment, analyses, and report writing). Each subject will be monitored for 6 months ( $\pm$  1 month).

#### **V. Potential Benefits**

1. Duration of PN in patients with surgical short bowel syndrome may be decreased
2. Incidence of central line infections in these patients may be decreased
3. Improving overall nutrition and growth
4. Improving the gut mucosal immunity with oral GLN

#### **VI. Potential Risks**

Potential risks for GLN supplementation:

- Stomach pain - 11%
- Nausea - 22%
- Tenesmus - 11%
- Pancreatitis - 11%
- Constipation - 11%
- Fever - 11%
- Gastric Ulcer - 11%
- Increased irritability - 11%
- Mild skin rash or itching - 11%
- Hyperammonimia in patients with renal and hepatic dysfunction - 11%
- Laryngitis/Pharyngitis - 11%

Other adverse events reported in the product information package

- Gastrointestinal fistula in patients with Crohn's disease - 11%

- Vaginal fungal infections – 11%
- Psychiatric disorders – 11%
- Pyelonephritis – 11%
- Vascular disorders- 11%

Potential risks for L-alanine (placebo):

- Nausea and vomiting - 11%
- Hyperammonimia in patients with renal and hepatic dysfunction - 11%

Potential risks for L-Glutamine and L-alanine

- Hyperosmolality of the feeds leading to increased stool output is a potential side effect of L-Glutamine and L-alanine when added to formula. However, this has not been reported in previous trials. The osmolality of L-glutamine is 310 mosm/kg of water (data provided by Emmaus Medical Inc).

Potential risks for blood draw:

- Occurrence of discomfort and/or a bruise at the site of puncture
- Less commonly, fainting
- The formation of a clot or swelling in the vein and surrounding tissue
- Bleeding from the puncture site
- On rare occasions an infection may develop at the site where the blood is collected

## VII. Overall Risk Assessment

The overall risk assessment is minimal based on previous pediatric and adult studies. The potential long term benefits of reducing the duration of PN, decreasing central line infections and improving growth is greater than the potential risks.

## VIII. Risk Category

Minimum

## IX. Methods

### A. Subjects and controls Selection

#### Inclusion criteria for age matched controls (n=12: 6 per site)

- Males and females will be recruited as controls for this study if they are  $\leq 12$  months of age (corrected for gestational age)
- Normal small bowel length without any intestinal resection or primary intestinal disease
- Not currently on TPN and if ever on TPN this should have been discontinued for at least 4 weeks

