
## II. Purpose of Study

This is a double-blind, randomized placebo-controlled pilot study to investigate the efficacy of enteral glutamine (GLN) supplementation in 36 infants,  $\leq 12$  months of age with parenteral nutrition (PN)-dependent short bowel syndrome (SBS) due to massive small bowel resection for NEC, omphalocele, gastroschisis and/or atresia on improving weaning of PN and preventing infections. We intend to evaluate the effect of enteral feeding and GLN supplementation on the gut bacteria. We will also recruit 12 age-matched controls to evaluate the normal gut bacteria. Investigators at the University of Michigan and Cincinnati Children's Hospital Medical Center will recruit the potential subjects (18 patients and 6 controls will be recruited at each site). We will estimate residual small and large bowel length and the presence, or absence of the ileocecal valve and colon by review of surgical records and postoperative intestinal barium studies in the subjects. Estimates of bowel length for gestational age have been previously published. Data on parenteral or enteral GLN supplementation (L-GLN or the dipeptide Alanyl-GLN) in infants have not shown consistent effects, potentially because these studies were under powered; the dose of GLN was suboptimal or other factors.

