#### Exclusion criteria for age matched controls

- Major congenital or chromosomal anomalies
- Inability to tolerate enteral nutrition/ regular cow's milk, breast milk or soy formula

- History of liver/intestinal transplantation
- Active milk protein allergy
- Inflammatory bowel disease
- Multiorgan failure

Inclusion Criteria for glutamine and placebo group of SBS patients (n=36; 18 per site)

- Males and females  $\leq$  12 months of age (corrected for gestational age)
- Patients who have undergone small bowel resection due to complications of or related to NEC, omphalocele, gastroschisis or intestinal atresia with known small bowel length
- Patients who have been PN dependent for more than 42 consecutive days (6 weeks) and currently on TPN at time of enrollment. This would include patients who were off TPN for  $<$  7 consecutive days.
- Patients who have the ability to take partial enteral nutrition of at least 5ml/hr breast milk or elemental formula (Elecare® is the preferred formula at both clinical sites but use of other elemental formula does not exclude the patient) (via gastric or intestinal tube, or orally) to allow the appropriate dose of GLN (0.6 g/kg/day) or placebo (L-alanine)
- Signed informed consent for the use of GLN or placebo obtained

Exclusion Criteria for glutamine and placebo group of SBS patients

- Major congenital or chromosomal anomalies
- Inability to tolerate enteral nutrition that will preclude treatment with enteral GLN or L-alanine placebo for  $>$ 2 consecutive weeks
- Liver/intestinal transplantation
- Multiorgan failure

B. Withdrawal Criteria

1. Patient cannot complete evaluation visit assessments
2. Patient develops any of the exclusion criteria detailed above
3. Patient develops significant hepatic dysfunction (defined as INR  $>$  2.5 or direct serum bilirubin level  $>$  10 mg/dL)
4. Parent(s)/legal guardian are unwilling to administer the GLN or placebo at the required dosage
5. Patient is lost to follow-up
6. Patient has 3 missed study visits
7. It is in the patients best interest

C. Dropouts

Data collected from patients who voluntarily withdraw from the study or who are withdrawn from the study will be included in the final analysis using intent to treat. Patient and control enrollment will continue until 32 patients complete all requested study requirements outlined. The reason for withdrawal will be documented.

D. Stopping Rules

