**Study procedures of control group:**

Healthy age-matched infants (n=12; 6 at each site) will have serial stools collected on 4 occasions, each separated by 60 days [baseline, days 60(±15), 120(±15) and 180(±15)]. This is abbreviated compared to the study subjects.

A week prior to the scheduled date of stool collection, families will receive a brief medical questionnaire and stool container. They will be instructed to complete the questionnaire and send in with the stool specimen.

They will be provided with a sterile container with instructions to collect stool and bring in to the clinic for storage and analysis. They will be asked to collect stool on the day of the next anticipated clinic visit, put the stool in a sterile container (which may contain RNAlater) which will be supplied to them by the study team. They will put this in a storage bag, keep cool and bring the sample to the clinic visit.

Parents/Primary caregivers drop off stool specimen to the research team at the study site or will arrange with the team for the specimen to be collected from their homes.

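### Controls are called age-matched but no matching rule is written, and the non-randomised SBS-versus-control microbiome comparison makes no allowance for age

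*Combined protocol and SAP*

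**What the plan says.** Section II (Purpose of Study) states the intention: "We will also recruit 12 age-matched controls to evaluate the normal gut bacteria". The control-group procedures in section IX.H repeat the label: "Healthy age-matched infants (n=12; 6 at each site) will have serial stools collected on 4 occasions". Section X, under Specific Aim 3, names the source: "Healthy age matched infants (n=12) will be recruited from the Gastroenterology and surgery clinics".

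The operative rule is in section IX.A. Its first control criterion, "Males and females will be recruited as controls for this study if they are" no more than 12 months old on the corrected scale, carries the same ceiling as the first criterion for SBS infants. Neither list contains a matching window, a pairing rule or an age quota.

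The statement of Specific Aim 3 tags SBS versus controls as the primary endpoint. A separate line in the same section gives the Aim 3 primary outcome as raised K. pneumonia and E. faecalis in SBS infants who have BSI.

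Section XIII, item 8, measures association for individual microbial groups by "comparing the abundances of these groups using the non-parametric Kruskal-Wallis test" and uses UniFrac for population-wide differences between SBS and control. Neither has an age term or strata. Elsewhere in section XIII age is a covariate, but only in the glutamine-versus-placebo models: cytokines, plasma glutamine, stool sIgA, enteral proportion and growth. The opening paragraph of section XIII adds a descriptive baseline summary of the control group.

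**The concern.** A shared upper age limit is not matching. Two groups can both lie within the first year and still differ by several months on average, and nothing in section IX.A stops that. SBS infants and controls arrive by different routes: one group is on parenteral nutrition after resection, the other is off it and attending a clinic for some other reason.

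This comparison is not randomised, so age must be handled by selection or by analysis. The plan claims the first without defining it and omits the second. It adjusts for age in the comparisons that randomisation already protects, and not in the one where nothing does. By choosing age-matched controls, the sponsor signals that age matters here. The documents give no figure for how strongly abundance varies with age.

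At stake is the reading of the SBS-versus-control result. A taxon that differs because the controls are older or younger would be reported as altered by SBS.

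**Working it through.** **No plan figure to reproduce.** The Sample size section covers BSI and cytokines only. No effect size, power or expected age distribution is given for SBS versus control.

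**Inputs.** From the documents: 36 SBS infants, 12 controls, two-sided 5%. Assumed: age SD 3 months in each group, correlation r between age and a taxon's abundance of 0.3, 0.5 or 0.7, and no true SBS effect.

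**Step 1: the age gap that chance alone produces.** SE of the difference in mean age = 3 × √(1/36 + 1/12) = 3 × √(4/36) = 1.0 month. If both groups are drawn from the same age distribution, a gap of 2 months or more in either direction (2 SE) arises in about 5% of trials, and 3 months or more (3 SE) in about 0.3%.

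**Step 2: a systematic gap.** Shift in abundance, in SD units = r × gap/3. Noncentrality λ = shift × √(36 × 12/48) × 0.977, where 0.977 = √(3/π) is the efficiency factor of the rank test under normality. Since √(36 × 12/48) = 3, λ = r × gap × 0.977. The chance of a significant result is Φ(λ − 1.96) + Φ(−λ − 1.96).

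| r | λ, 2-month gap | significant | λ, 3-month gap | significant |
|---|---|---|---|---|
| 0.3 | 0.586 | 9% | 0.879 | 14% |
| 0.5 | 0.977 | 16% | 1.466 | 31% |
| 0.7 | 1.368 | 28% | 2.052 | 54% |

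**Step 3: simulation with assumed age ranges.** 4,000 trials per row, uniform ages, no SBS effect, Kruskal-Wallis at 5%. Here r is scaled to the SD of a uniform 0 to 12 month range (3.46 months).

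| SBS ages (months) | Control ages (months) | Gap in means | r = 0.3 | r = 0.5 | r = 0.7 |
|---|---|---|---|---|---|
| 0–12 | 0–12 | 0 | 5% | 5% | 4% |
| 1.5–12 | 0–12 | 6.75 − 6 = 0.75 | 5% | 6% | 7% |
| 1.5–8 | 4–12 | 8 − 4.75 = 3.25 | 12% | 32% | 62% |
| 1.5–6 | 6–12 | 9 − 3.75 = 5.25 | 26% | 67% | 97% |

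Every row is compatible with the written age criteria. The second row treats the parenteral nutrition requirement as an age floor of about six weeks for SBS infants only.

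**Step 4: with age in the model.** In the same simulations, a linear model with group and age gave 4 to 6% in every scenario. Age acts linearly in the simulation, so this is a favourable setting for adjustment.

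**The case against.** The best defence is that the distortion is conditional. If controls happen to resemble SBS infants in age, the planned test keeps its level (step 3, first row), and the baseline summary of controls would reveal an imbalance. Both statements are right, but a visible imbalance is still not corrected by anything in the plan.

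It can also be said that section XIII ties only UniFrac explicitly to SBS versus control. Kruskal-Wallis is assigned to treatment arms and main outcome measures. The percentages above are for a rank test, and no figure is offered for UniFrac. The omission of age is common to both.

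Several stronger readings are tempting and are not supported:

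- **That 12 controls make a material age gap likely.** Step 1 shows that chance rarely gives 2 months. The concern is a systematic difference between recruitment streams, and the documents neither show one nor guard against one.
- **That the entry rule "Patients who have been PN dependent for more than 42 consecutive days (6 weeks) and currently on TPN at time of enrollment" makes SBS infants older.** Those 42 days run on postnatal time, whereas eligibility uses corrected age. Taking term as 40 weeks, an infant born at 34 weeks completes six weeks of parenteral nutrition at corrected age zero at the earliest. Even treated as a true floor, the rule moves the error rate only to 5 to 7%.
- **That clinic-recruited controls have abnormal flora.** Section IX.A requires normal bowel length without resection or primary intestinal disease. It excludes inflammatory bowel disease, active milk protein allergy, feeding intolerance and major anomalies. Calling them healthy is loose, since past TPN is allowed if stopped at least four weeks earlier, but that is mostly labelling.
- **That the trial's main result is at risk.** The BSI primary outcome and all randomised comparisons are outside this point, as is the Aim 3 primary outcome within SBS infants.

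**Conclusion.** The point stands in limited form. The plan claims age matching, defines none, and makes no allowance for age in the one comparison that randomisation does not protect. A systematic age difference between the streams would therefore be indistinguishable from an SBS effect.

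The size cannot be fixed from the documents. The ranges of 9 to 28% at a 2-month gap and 14 to 54% at 3 months rest on an assumed gap, an assumed SD of 3 months and assumed correlations of 0.3 to 0.7. They illustrate sensitivity and are not an expected error rate. With like ages the rate is near 5%. The change is still worth making, because the comparison carries a primary-endpoint tag and the remedy needs no more infants and no new data.

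**What to change.** **Section IX.A (control selection).** Define the matching. Set corrected-age bands in advance, for example 0–3, 3–6, 6–9 and 9–12 months, and fill control places in proportion to SBS infants enrolled to date in each band. The overall ratio is 36/12 = 3 (18/6 = 3 per site), so roughly one control place opens for every three SBS infants in a band. Bands fixed beforehand avoid waiting for the final SBS age distribution.

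**Section XIII, item 8.** State which tests apply to SBS versus control, and make them age-stratified or age-adjusted: a rank test stratified by band or a model with age as covariate, and UniFrac permutations restricted within bands. Add a sensitivity analysis on postnatal age, because eligibility uses corrected age and the groups may differ in prematurity.

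If controls are already enrolled, the analysis change alone suffices, although a band holding only one group adds nothing to a stratified test.

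**Cost.** Recruitment-log wording and SAP text. Control enrolment will trail SBS enrolment somewhat, and spreading 12 controls over bands loses a little precision.
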